#### *Multiple imputation for HFMSE , upper limb module test endpoint, PedsQL and ACEND*

Since month 15 HFMSE score values will not be available for many of the patients at the interim analysis, missing data will be handled using the multiple imputation (MI) method (Schafer 1997; Schafer 1999). The same method for imputation of missing values will be used at the final analysis.

The imputations will be performed on total scores for baseline and post-baseline visits. The Markov Chain Monte Carlo (MCMC) method will be used under the multivariate normality assumption to impute the missing score by treatment group. The treatment variable will be coded so that the ISIS 396443 group is the first in the sort order and therefore as the MI procedure is by treatment the imputation will be performed on ISIS 396443 subjects first.

Prior to the Proc MI step the dataset will be sorted by treatment and then ascending unique subject identifier (USUBJID). The variable list for imputations will include the baseline total score, age at consent, as well as all available post-baseline total scores. A set of 100 complete imputed data sets will be generated and the relative efficiency (RE) parameter will be checked. The RE is a very common parameter used in MI to determine the acceptability of the imputed results. Regarding the number of imputations, since the sample size in this study is relatively small and proportion of missing information is large, it will be important to run a large number of imputations to get an RE that is close to 98% or higher.

For PedsQL and ACEND the imputation will be performed independently on each dimension or summary score (constructed using all, or a subset of dimensions) separately, rather than at the item level.

The following pseudo SAS code and seeds will be used to perform the multiple imputation.

```
proc mi data =in_data    seed = x n impute = 100 out= imp_data;
  mcmc chain = multiple;
  var base age D92 D169 D274 D365 D456;
  by treatment;
  run;
```

---

Endpoint	Seed
HFMSE	25980495
Upper limb module test	47886416
PedsQL Core Parent	
Physical functioning	12676424
Emotional functioning	35764041
Social functioning	85032085
School functioning	79256650
Psychosocial health summary	74500750
Total Score	51407567
PedsQL Core Patient	
About my health and activities	48001267
About my feelings	21787096
How I get along with others	95088062
About School	11511569
Total Score	13067474
PedsQL Neuromuscular Parent	
About my child's neuromuscular disease	33325144
Communication	27244614
About our family resources	84519141
Total Score	49741400
PedsQL Neuromuscular Patient	
About my neuromuscular disease	90156114
Communication	62901627
About our family resources	17014549
Total Score	76235199
ACEND	
Domain I – Feeding/Grooming/Dressing	68757534
Domain II – Sitting/playing	14107127
Domain III – Transfer	54836220
Domain IV – Mobility	96063155
Domain V – Time	38462550
Domain VI – Emotion	85339274
Domain VII - Finance	70873601

---

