## **2 Study design**

This is a Phase 3, multicenter, double-blind, randomized, sham-procedure-controlled study of ISIS 396443 administered intrathecally over 15 months to patients with later-onset SMA. Approximately 117 subjects will be randomized 2:1 to receive a 12 mg dose of ISIS 396443 or undergo a sham procedure as control, respectively. Randomization will be stratified based on the subject's age at screening: <6 years versus  $\geq$ 6 years. A separate randomization list will be used for Japan. If a subject does not successfully receive the first dose of ISIS 396443 or undergo the first sham procedure, they will be replaced.

ISIS 396443 will be administered using a loading regimen (dosing on Study Days 1, 29, and 85) followed by a maintenance dosing 6 months thereafter (Day 274). Subjects randomized to the sham-procedure control group will undergo a sham-procedure on Study Days 1, 29, 85, and 274.

No adjustment of dose is permitted. However, should a concurrent illness prevent the dosing procedure from being performed safely, each scheduled dose may be delayed by up to 4 weeks.

The study will consist of screening, treatment, and post-treatment follow-up-periods. The total duration of participation in the study is approximately 16 months.

Blinded safety data will be reviewed on an ongoing basis by the Sponsor and the Medical Monitor. Unblinded safety data will also be reviewed on an ongoing basis by an independent Data Safety Monitoring Board (DSMB) (Section 6.6). In the protocol it was planned that an interim analysis may be conducted when all subjects will have completed the month 6 assessment and at least 39 will have completed the month 15 assessment. An interim efficacy analysis will be conducted using a targeted cut-off date of 31 August 2016 for the clinical data. At the time of the interim analysis, it is expected that approximately 52 subjects will have attended the Month 15 assessment and all 126 subjects will have had the opportunity to attend the assessment at Month 6 (Section 5.1).

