### 5.1 Interim and final efficacy analyses

An interim analysis may take place when all subjects have completed the 6-month assessment and at least 39 subjects have completed the 15-month assessment with a targeted clinical cut-off date of 31 August 2016. At the interim analysis, only the primary endpoint will be tested. The final efficacy analysis will take place when the last subject completes the 15-month assessment or earlier if the study is terminated on the grounds that conducting a sham-controlled study is no longer deemed ethical based on the assessment of risk-benefit of ISIS 396443.

At the interim analysis and final analysis, the same analysis of covariance (ANCOVA) model will be used in analyzing the change from baseline in HFMSE score to month 15. At the interim analysis, the month 15 endpoint values will not be available for some patients, so a multiple imputation method will be used to estimate them ([Section 5.3](#)). This method will also be used in the final analysis for the primary endpoint

The interim analysis results will be reviewed by an independent Data Safety Monitoring Board (DSMB) and an Unblinded Senior Management Team from the Sponsor. Recommendation will be made on whether it is appropriate for the trial to continue according to the current protocol or whether the protocol needs to be modified. During the interim analysis, subjects will continue in the study.

In the protocol it had been planned to conduct the interim efficacy analysis with an alpha of 0.02, however in finalizing this statistical analysis plan it was decided to conduct the interim analysis at a significance level of 0.025. If the study is not stopped at the interim analysis, the final analysis (test and confidence interval estimate procedures) will be conducted at a significance level determined by the resampling procedure as follows.

Let  $T_1$  and  $T_2$  be the standardized test statistics at the interim and final analyses, respectively. In order to determine the alpha level for the final analysis, the correlation between  $T_1$  and  $T_2$  is first estimated based on the resampling approach (Westfall and Young 1993):

- Among the 126 subjects enrolled in the study, randomly assign 84 subjects to the ISIS 396443 group and 42 subjects to the sham control group.
- Apply the re-randomized treatment assignment to the interim data and obtain the standardized test statistics  $T_1$ .

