In the event of a decision by the study Sponsor to terminate the study earlier on the grounds that conducting a sham-controlled study is no longer deemed ethical based on an updated risk-benefit assessment of ISIS 396443 from the planned interim analysis, all subjects will be invited for the EODBP study visit, during which all Day 456 assessments will be conducted. The EODBP visit should occur no less than 2 weeks from the most recent dosing/sham procedure administered. After completing the EODBP visit, subjects will be considered study completers and will be allowed to enroll into the OLE study. Under this scenario, since patient participation and monitoring continue until the study is stopped, the final analysis that incorporates the accrued data will be conducted. At the final analysis, the primary efficacy endpoint will not be tested again since significance has already been achieved at the interim. The secondary endpoints will be tested at an alpha of 0.05 as shown in the diagram below.

In a scenario where the primary efficacy endpoint is not significant at the interim analysis, no additional data will be evaluated. In this case, at the final analysis, the primary endpoint will be tested at an alpha level determined based upon the resampling approach method. If the primary endpoint is not significant at the final analysis, then the testing of the secondary endpoints will be considered exploratory. If the primary endpoint is significant at the final analysis, then the secondary endpoints will be tested at an alpha of 0.05 as shown in the diagram below.

In the event that a secondary endpoint is not significant and formal testing is ended, the remaining endpoints will be tested but the results will be considered exploratory.

Analyses of tertiary efficacy endpoints will not include adjustments for multiplicity.

The analysis of safety data for the interim analysis will include all subjects who have received at least one dose of study treatment as of the targeted clinical cut-off date.

Although statistical stopping guidelines have been pre-specified for the interim analysis, a number of factors must be considered thoroughly as part of the decision to modify or stop the study. A recommendation to modify or stop the study will, therefore, not be based solely on statistical grounds.

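### At 100 imputations the relative-efficiency check in SAP 5.3 is always met and says nothing about p-value stability; 1000 for HFMSE would cut simulation noise in the interim test about threefold (low severity)

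*SAP*

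**What the plan says.** SAP 5.3 imputes missing HFMSE totals by MCMC under a multivariate normal model, separately by arm. On the number of imputations it says: "A set of 100 complete imputed data sets will be generated and the relative efficiency (RE) parameter will be checked". It notes that the sample is small and the share of missing information large, and concludes that "it will be important to run a large number of imputations to get an RE that is close to 98% or higher". The code hard-codes the number ("seed = x n impute = 100 out= imp_data"). The HFMSE seed (25980495), the sort order and the arm order are all written down. The figure 100 recurs twice in the analysis-methods part of 5.3 and once in 5.5.2.2. The rule covers both analyses: "The same method for imputation of missing values will be used at the final analysis".

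SAP 2 expects that at the interim "approximately 52 subjects will have attended the Month 15 assessment and all 126 subjects will have had the opportunity" to attend Month 6. SAP 5.1 tests the primary endpoint at the interim, two-sided at 0.025, and adds: "If the study is not stopped at the interim analysis, the final analysis (test and confidence interval estimate procedures) will be conducted" at a level found from 10,000 re-randomisations. SAP 5.2 deals with early termination after the interim. "Under this scenario, since patient participation and monitoring continue until the study is stopped", a final analysis of the accrued data follows, but "the primary efficacy endpoint will not be tested again since significance has already been achieved at the interim".

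**The concern.** RE is the only criterion the plan states for whether 100 imputations are enough. A criterion that is satisfied before any data exist gives no assurance. RE also answers a different question: it compares the variance of the pooled estimate at m imputations with that at infinitely many. The interim test needs something else, namely that the p-value would be nearly the same had another seed been written into the SAP. Well over half the endpoint values are expected to be imputed, and they feed one test that becomes the confirmatory one if the study then stops. If the p-value lands close to 0.025, part of the call is simulation noise that more computing would remove.

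**Working it through.** **1. The plan's own figure.** RE = 1/(1 + FMI/m). At m = 100, RE is 0.997 for FMI 0.3, 0.994 for FMI 0.6, and 1/1.01 = 0.990 at the limit FMI = 1. To fall below 98% at m = 100, FMI would have to exceed 100 × (1/0.98 − 1) = 2.04, which is impossible. From m = 49 the target is met for any FMI, since 1/(1 + 1/49) = 0.98. The plan's figure is reproduced, and it is guaranteed.

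**2. Inputs for the noise.**
- Expected imputed share at the interim: 126 − 52 = 74, and 74/126 = 59% (SAP 2).
- Two-sided 0.025 gives a critical z of 2.241 (SAP 5.1).
- Allocation 84:42 (SAP 5.1); effect 3 points and SD 4.4 (SAP 9).
- FMI is not in the documents. I assume 0.3 to 0.6, because earlier visits recover part of the missing information.

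**3. Noise at the boundary.** Var(z) = FMI/m + (z²/4) × FMI² × 2/(m − 1). The first term is noise in the pooled estimate, the second noise in the between-imputation variance. SD(p) = 2φ(z) × SD(z), with 2φ(2.241) = 0.0647. Example, FMI 0.6 and m = 100: 0.0060 + 1.256 × 0.36 × 0.0202 = 0.0151, so SD(z) = 0.123 and SD(p) = 0.0080.

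The last two columns give the chance that two seeds disagree about significance at the design effect. Mean z is 3/(4.4 × √(1/84 + 1/42)) × √(1 − FMI), that is 3.02, 2.79, 2.55 and 2.28, and the rate follows by integration.

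| FMI | SD(z), m=100 | SD(p), m=100 | SD(z), m=1000 | SD(p), m=1000 | Disagree, m=100 | Disagree, m=1000 |
|---|---|---|---|---|---|---|
| 0.3 | 0.073 | 0.0047 | 0.023 | 0.0015 | 2.4% | 0.8% |
| 0.4 | 0.090 | 0.0058 | 0.028 | 0.0018 | 3.5% | 1.1% |
| 0.5 | 0.107 | 0.0069 | 0.034 | 0.0022 | 4.6% | 1.4% |
| 0.6 | 0.123 | 0.0080 | 0.039 | 0.0025 | 5.5% | 1.7% |

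Under the null, disagreement at m = 100 is 0.5% to 0.9%.

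**4. Simulation check.** By-arm normal imputation, ANCOVA and Rubin's rules were run with an assumed 126/126/105/78/52 subjects observed at the five visits, under six correlation patterns. Mean FMI was 0.38 to 0.58. SD(z) was 0.097 to 0.134 at m = 100 and 0.029 to 0.041 at m = 1000; SD(p) at m = 100 was 0.007 to 0.009. This is somewhat above the formula, hence the rounded range of 0.07 to 0.13.

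Five further simulated interim datasets had FMI 0.39 to 0.63, and RE was never below 0.9927. In one, with a long-run p of 0.0258, the middle 95% of seeds at m = 100 gave p from 0.013 to 0.044, and 41% fell below 0.025. At m = 1000 the range was 0.022 to 0.031. Across the five, SD of the pooled statistic fell 2.9- to 3.5-fold, in line with √10 = 3.16. The dataset with the highest FMI (0.63) gave 0.165 at m = 100, so the noise is larger beyond the assumed range.

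**5. Where it matters.** At least 5% of seeds change the call only if the long-run z is within 1.645 × SD(z) of 2.241. At m = 100 that is p from 0.018 to 0.034 (FMI 0.3), or 0.015 to 0.041 (FMI 0.6). At m = 1000 and FMI 0.6 it narrows to 0.021 to 0.029.

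**6. Estimate and power.** The Monte Carlo SE of the pooled difference is √(B/m), with B = FMI × 0.8315²/(1 − FMI). It is 0.05 to 0.10 HFMSE points at m = 100 and 0.02 to 0.03 at m = 1000, against a 3-point effect. Scaling mean z by 1/√(1 + FMI/m) and adding the noise, m = 100 costs about 0.2 to 0.3 percentage points of interim power against an unlimited m.

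**7. Resampling step.** Keeping 100 imputations inside the re-randomisations lowers the interim–final correlation by about 0.45% at FMI 0.6. The final level moves from 0.02890 to 0.02886 (correlation 0.5) or from 0.03715 to 0.03699 (correlation 0.8). The change is at most about 0.0002 and conservative.

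**8. Final analysis.** With about 10% missing (12 of 117, assumed from the gap between 117 enrolled and 105 in the power calculation), SD(z) is about 0.035 at m = 100 and 0.011 at m = 1000.

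**The case against.** Only one seed will ever be run, and it is named in advance, so the two-seed disagreement rate describes an event that does not occur in the trial. The noise variance, 0.073² to 0.123², is only 0.5% to 1.5% of the sampling variance of z. The RE sentence can be read as a reason for choosing a large m, and no decision hangs on it. The interim also includes seed-free analyses: MMRM without imputation, completers and LOCF (SAP 5.5.2.2 and 5.5.3). Stopping does not rest on statistics alone (SAP 5.2), and filing rests on the totality of the data (SAP 5.9). One can add that a reported Monte Carlo error with no limit attached cannot fail either.

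Nearly all of this stands, and it is why the point is minor. It does not make RE informative. A Monte Carlo error at least tells the reader how far the p-value could have moved, which RE does not.

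A reader might infer that the interim could be won by picking a seed, or that its false-positive rate exceeds 0.025. The documents do not support this: m, seed, sort order and arm order are all prespecified. A reader might also infer that a significant interim always settles the primary endpoint. The sentence that rules out a retest is written for early termination; SAP 5.1 sends a study that is not stopped to a final test at the resampled level.

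**Conclusion.** The point holds as a low-severity, cheap improvement and not as a validity problem. Two parts need no assumption about the data: RE is at least 0.990 at m = 100, and going to m = 1000 cuts the simulation noise by about √10. The absolute size (SD of z roughly 0.07 to 0.13, SD of p roughly 0.005 to 0.009) rests on the assumed FMI and, in the simulations, on assumed visit correlations and follow-up. It is of practical consequence only for an interim p between about 0.015 and 0.04. At the final analysis the noise is already small, so the case for changing m there is consistency alone.

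**What to change.** Before the interim data are unblinded:

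1. Use 1000 imputations for HFMSE at the interim, and at the final analysis only so that the method stays the same. Keep seed 25980495, the sort order and the arm order. Upper Limb, PedsQL and ACEND can stay at 100.
2. Change the hard-coded 100 for HFMSE in the text and code of SAP 5.3, in both places in its analysis-methods part, and in 5.5.2.2. The responder endpoint in 5.6.1.1 uses the same datasets and needs no new wording.
3. State in SAP 5.1 that each of the 10,000 re-randomisations uses 100 imputations. Otherwise, if imputation is rerun each time for both statistics (the SAP does not say), the load goes from 10,000 × 2 × 100 = 2 million imputed sets to 20 million.
4. Replace the RE sentences with a commitment to report the Monte Carlo SE of the pooled treatment difference, √(B/m), and that of the pooled z or p-value by a named method, such as a jackknife over imputations.

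The cost is a few lines of text and about ten times the computing for every analysis that uses the HFMSE imputed sets: main, per-protocol and fifth sensitivity analyses, by-visit analyses, responder endpoint and subgroups.

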### *Multiple imputation analysis methods*

For the HFMSE, PedsQL, ACEND, upper limb module the imputations will be performed on the ITT population. In any sensitivity analyses using multiple imputation such as repeating the main analysis in the PPS the subset of subjects in the PPS will be selected from the multiple imputed datasets obtained from the ITT population. If the MI procedure imputes any

values outside the expected range for the scale e.g. from 0 to 66 for HFMS-E then values below 0 will be set to 0 and values above 66 will be set to be 66.

For each of the 100 imputed datasets, the endpoint will be compared between treatment groups using an ANCOVA model for continuous endpoints or logistic regression for binary endpoints as described in the main analysis for each endpoint. The estimates from the 100 fitted models will be combined to provide an overall estimate with corresponding confidence intervals and p-value [Little et al, 2002].

For the continuous endpoints, the difference between treatments and the corresponding CI will be presented. In addition, for each subject the median change from baseline to each visit will be calculated across the multiple datasets and summarized by treatment group. For the analyses using logistic regression the odds ratio and corresponding CI will be presented. In addition, the estimates of the binomial proportions in each treatment arm and the differences between treatments will be presented (Ratitch, 2013).

If, due to a small sample size or other unforeseen scenario, the multiple imputation model does not converge or encounters computational difficulties, then the number of iterations will be increased. If the model still fails then a Mixed Effects Model with Repeated Measures will be used as the primary analysis as described in Section 5.5.1.2.

In the presentation of results from multiply imputed data, the number of subjects with missing data and the degree to which it is missing will be summarized.

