### 3 General considerations

In this Statistical Analysis Plan, the terms “control” and “control group” refer to the set of subjects who were randomized to undergo the sham procedure, and the terms “treatment” and “dosed” are used interchangeably to describe those subjects in the ISIS 396443 group who received at least one intrathecal injection of ISIS 396443.

In order to distinguish nominal visit names from duration defined in terms of days, visit names will be referred as “Day 29”, “Day 85,” etc., and “29 days” or “85 days,” etc. will be used to define time intervals. In the protocol definitions of the efficacy endpoints, and description of the interim analysis, “Month 6” is used to refer to “Day 169” and “Month 15” is used to refer to “Day 456” and this convention will be followed in this SAP.

The Intent-to-treat (ITT) Set and the Per-protocol Set (PPS) will be used for the efficacy analyses. The ITT Set is defined as all subjects who are randomized and received at least one dose of study drug/sham procedure. Subjects will be analyzed in the treatment group to which they were randomized. This will be the primary population for the analysis of efficacy endpoints.

An Interim Efficacy Set will be defined for presentation of the WHO motor milestone endpoints in the event an interim analysis is performed. The Interim Efficacy Set will be defined as the subset of subjects in the ITT Set who have the opportunity to be assessed at the Month 15 visit. Specifically, the Interim Efficacy Set will include all subjects with a Month 15 visit and all subjects with time difference of at least 463 days (456 plus 7 day window) between date of first dose and the targeted clinical cut-off date for the interim analysis (i.e., dosed on or before May 27, 2015). However, a subject who has died or withdrawn will be included provided that there is a time difference of at least 449 days (456 minus 7 day window) between the date of first dose and the targeted clinical cut-off date of Aug 31, 2016 for the interim analysis (i.e., dosed on or before June 10, 2015).

In the event of the study being stopped early, an Efficacy Set will be similarly defined for the analysis of motor milestones. If, however, the study continues to completion as planned, the ITT Set will be used for the final analysis of motor milestones.

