The PPS will include the subset of the ITT who complete at least the initial 3 doses of study drug/sham procedures, have baseline and Day 169 efficacy assessments and who have no significant protocol deviations that would be expected to affect efficacy assessments.

Significant protocol deviations will be determined prior to database lock but will include subjects who had onset of signs and symptoms consistent with SMA at less than or equal to 6 months of age, who cannot sit independently, whose HFMSE is <10 or >54 at screening, who had respiratory insufficiency at Screening (defined as medical necessity for invasive or non-invasive ventilation for >6 hours during a 24-hour period), and subjects who took any medicines (such as valproate, riluzole, creatine, sodium phenylbutyrate, hydroxyurea, salbutamol, olesoxime) during the study for the treatment of SMA, shown to modulate SMN gene expression or SMA disease progression in humans or preclinical models. The Safety Set, comprised of all subjects who were randomized and received at least one dose of study drug or underwent one sham procedure, will be used for the analysis of safety data. Subjects

randomized to receive sham procedure, incorrectly treated with ISIS 396443 will be counted in the ISIS 396443 group from the first dose of ISIS 396443 received.

The Pharmacokinetic Population is comprised of all subjects who were randomized and for which there is at least one evaluable post-dose/post-sham procedure pharmacokinetic sample. Analysis of immunogenicity data will also be based upon this population.

A listing denoting inclusion/exclusion of patients in all the analysis populations will be provided.

The individual sites in this multicenter study will be pooled for the purpose of statistical analysis.

Summary statistics will be presented throughout. For continuous endpoints, the summary statistics will generally include number of subjects with data, mean, standard deviation, median, minimum and maximum. For categorical endpoints, the summary statistics will generally include: number of subjects randomized and/or dosed, number of subjects with data, and the percentage of those with data in each category. Frequency distributions will be presented as appropriate.

The statistical software, SAS® version 9.3 or above, will be used for all summaries and statistical analyses.

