#### **5.5.2.2 Sensitivity analyses**

The sensitivity analyses planned for the final analysis of the primary endpoint will be repeated at the interim with the exception of the PPS analysis.

The analysis of subjects with non-missing Month 15 values described for the primary endpoint will be performed at 15 months, but it is noted that since this is an interim analysis the number of subjects available will be small so this is included to explore the trend.

One exploratory analysis using the same ANCOVA model as the primary analysis may be performed based upon the IES. In the event a subject is in the IES but has a missing value at 15 months then the median value for the subject at Month 15 across the 100 datasets from the multiply imputed data will be used in the imputation.

The exploratory analyses outlined in Section 5.5.1.3 will be performed at the interim on the ITT Set using the imputed dataset from the main analysis.

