### **5.6.7 Interim Analysis**

No testing of the secondary endpoints will be performed at the interim but summary statistics for each measure may be provided as follows. For the HFMSE and upper limb endpoints the multiple imputation approach will be used as described in the main analysis, based on the ITT Set. For the endpoints evaluating WHO motor milestones, the analysis will be performed as described but based on the IES. To further explore the response in the cohort of subjects in the IES for the HFMSE and upper limb endpoint the main analysis will be repeated. In these analyses if Month 15 is missing then the median of the MI values will be imputed. For HFMSE if the reason for the missing Month 15 value is treatment failure or death then they would be set to be a non-responder and this would override any imputation.

As an exploratory analysis for the WHO milestones the main analysis will be conducted based on data from Month 6, Month 9 and Month 12, separately. Specifically, let  $X$  denote Month 6, Month 9, or Month 12. The evaluable set at the interim analysis for the Day  $X$  visit is defined as the subset of subjects in the ITT Set who have the opportunity to be assessed at the Day  $X$  visit. Specifically, it will include all subjects with Day  $X$  visit and all subjects with time difference of at least  $X+7$  days between the date of first dose and the targeted clinical cut-off date of Aug 31, 2016 for the interim analysis. However, a subject who has died or withdrawn will be included provided that there is a time difference of at least  $X-7$  days between the date of first dose and the targeted clinical cut-off date of Aug 31, 2016 for the interim analysis.

In a situation where an interim analysis is performed and a subject is in the evaluable set for a summary of WHO milestones but has missing data at this visit then this will be imputed using the rules in Section 5.6.2 up to the last visit at which a subject qualifies for inclusion in an evaluable set. So a subject who is in the Month 12 evaluable set but not the IES and has a missing value at Month 12 then this will be imputed but a Month 15 value will not be imputed.

In the event of a successful interim and subjects rolling over early to open label treatment, for the early final analysis the secondary endpoints will be evaluated as described for interim and evaluable sets for Month 6, Month 9, and Month 12 visits will be similarly defined as subsets of the ITT Set.

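### SAP 5.5.2.2 and 5.6.7 fill missing Month 15 values in the Interim Efficacy Set with a per-child median over 100 imputations, which is single imputation; in SAP 5.3 the same median understates the interim spread (minor)

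*SAP*

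**What the plan says.** SAP 5.3 (Multiple imputation analysis methods) fits the model in each of 100 imputed datasets and combines the estimates into one difference, confidence interval and p-value. As an added description of the continuous endpoints, "for each subject the median change from baseline to each visit will be calculated across the multiple datasets and summarized by treatment group". SAP 3 says that for continuous endpoints "the summary statistics will generally include number of subjects with data, mean, standard deviation, median, minimum and maximum", so an SD is likely in that table but not promised.

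At the interim, SAP 2 expects that "approximately 52 subjects will have attended the Month 15 assessment and all 126 subjects will have had the opportunity" to attend Month 6.

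The median returns in two places as a replacement value. In SAP 5.5.2.2, "One exploratory analysis using the same ANCOVA model as the primary analysis may be performed based upon the IES", and where a child in that set lacks a Month 15 score, "the median value for the subject at Month 15 across the 100 datasets from the multiply imputed data will be used". SAP 5.6.7 tests no secondary endpoint at the interim but says that "summary statistics for each measure may be provided as follows". It then repeats the HFMSE and upper limb analyses in the IES: "In these analyses if Month 15 is missing then the median of the MI values will be imputed". A non-responder rule for treatment failure or death overrides this for HFMSE.

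For the Per-protocol Set, SAP 5.3 does something different. It selects those children from the 100 imputed datasets and runs the usual combined analysis.

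**The concern.** Multiple imputation gives each missing score a prediction plus random residual noise, and repeats this so that the uncertainty reaches the standard error. A median over the 100 repeats undoes both steps. One number near the prediction remains, and it is then treated as if it had been observed.

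Two outputs follow from this. The IES analyses have standard errors without the between-imputation variance. An SD by arm in the 5.3 summary mixes real scores with nearly noise-free predictions, so responses look more uniform than they are. That table may be read when it counts: SAP 5.2 says that a recommendation to stop will not rest on statistical grounds alone, and SAP 5.9 bases the filing decision on the totality and consistency of the data. The plan gives no reason for handling the IES differently from the Per-protocol Set.

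**Working it through.** **1. The plan's own figure.** The documents give no SD for the per-child medians. The input that matters is the design SD of 4.4 (SAP 9), and the power built on it reproduces. SE = 4.4 × √(1/70 + 1/35) = 0.911; 3/0.911 = 3.29; normal power = Φ(3.29 − 1.96) = 0.909. The t-test with 103 df gives 0.904, against a stated 90% or more.

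**2. Share imputed at interim Month 15.** 126 − 52 = 74, and 74/126 = 58.7%. With the 84:42 allocation of SAP 5.1 and attendance assumed proportional, 35 of 84 active and 17 of 42 sham children are observed. The imputed shares are 49/84 and 25/42.

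**3. Closed form for the SD of medians.** If the median equals the prediction, SD = 4.4 × √(1 − f + f·R²). Here f is the imputed share and R² is the share of Month 15 variance explained by the child's observed data. R² is assumed. With f = 74/126:

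| R² | ratio | SD | too low by |
|---|---|---|---|
| 0.3 | 0.767 | 3.4 | 23% |
| 0.5 | 0.840 | 3.7 | 16% |
| 0.7 | 0.908 | 4.0 | 9% |
| 0.9 | 0.970 | 4.3 | 3% |

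In a completed final analysis with 10% missing (assumed) and R² = 0.3, the ratio is √(1 − 0.10 × 0.7) = 0.964, or 3.6% too low. The problem therefore belongs mainly to the interim.

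**4. Simulation.** The formula ignores error in the fitted predictions, which puts some spread back, so two simulations were run. Both used the counts in step 2, imputation by arm, 100 imputations, clipping to 0–66, missingness unrelated to outcome, and the unobserved children last seen at Day 169, 274 or 365 in equal shares. A used multivariate normal data augmentation (200 trials; R² from visits to Day 169 / to Day 365 shown). B used Bayesian regression visit by visit (300 trials; correlation r per 91 days). Entries are ratios to the complete-data SD.

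| Setting | Medians, active | Medians, sham | Within-dataset SD, active | Within-dataset SD, sham |
|---|---|---|---|---|
| A 0.19/0.48 | 0.818 | 0.856 | 1.046 | 1.093 |
| A 0.39/0.70 | 0.870 | 0.893 | 1.018 | 1.055 |
| A 0.75/0.91 | 0.957 | 0.958 | 1.006 | 1.016 |
| B r = 0.6 | 0.778 | 0.839 | 1.10 | 1.28 |
| B r = 0.8 | 0.849 | 0.881 | 1.07 | 1.18 |
| B r = 0.9 | 0.908 | 0.938 | 1.03 | 1.11 |
| B r = 0.95 | 0.950 | 0.955 | 1.02 | 1.05 |

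The SD of medians is 4% to 22% too low. The SD averaged within datasets errs the other way in sham, by 2% to 28%. The observed-data SD in A averaged 0.986 to 0.999 of the complete-data value.

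**5. Standard errors in the IES.** The set consists of children with a Month 15 visit or with enough time to have had one. In addition, "a subject who has died or withdrawn will be included provided that there is a time difference of at least 449 days" from first dose to cut-off. Few values should be missing, and the number is assumed. The ratio of the ANCOVA standard error after median filling to that by Rubin's rules, across the three settings of A:

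| Missing, added to 52 attenders | Seen to Day 365 | Last seen Day 169 |
|---|---|---|
| 2 | 0.979, 0.987, 0.996 | 0.965, 0.971, 0.989 |
| 6 | 0.936, 0.962, 0.989 | 0.902, 0.929, 0.968 |

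B, with 3 of 55 missing and seen to Day 365, gave 0.943 to 0.990. The shortfall is thus 0.4% to 9.8%. The logistic regression for the 3-point responder endpoint was not quantified.

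**The case against.** The 5.3 median is an added description with no inference attached, and an SD is only generally shown. The SD of per-child medians is a valid statistic if it is called that. This stands, and it is why labelling is enough there.

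The plan also has safeguards: a summary of missing data (5.3), HFMSE tables of observed values (5.5.1.3), and completers and MMRM analyses at the interim (5.5.2.2, 5.5.3). These limit the harm but do not correct the SD of medians or the IES standard errors.

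The size is uncertain, and the closed form runs high. Averaging 0.19 and 0.48 gives R² = 0.335, for which the formula returns 0.782 (active) and 0.777 (sham), against 0.818 and 0.856 simulated. This stands, so the simulated range should be quoted.

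Three stronger readings are tempting.

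- A reader might infer that the primary p-value is too small. If medians were analysed as data in the whole ITT Set, the standard error would be only 44% to 80% of the combined one in B. The SAP does not plan this: 5.5.1.1 and 5.5.2.1 use combined multiple imputation.
- A reader might infer that the median enters confirmatory testing after an early stop. The last paragraph of 5.6.7 sends the secondary endpoints to the interim methods, and 5.2 then tests them at 0.05. But the main method in 5.6.7 for HFMSE and upper limb is multiple imputation on the ITT Set, and the IES repeat is there for further exploration. The text supports this, though it could say so outright.
- A reader might infer that 5.5.2.2 turns the observed-value table of 5.5.1.3 into an imputed one at the interim. This is strained, because a table defined by observed values remains observed.

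**Conclusion.** The plan is wrong as written, with minor consequences. The median substitution in 5.5.2.2 and 5.6.7 makes exploratory standard errors too small with certainty of direction, but the loss is small and rests on assumed counts of missing values. Both analyses are optional in effect: 5.5.2.2 says so, while 5.6.7 states its repeat as firm but places it under summaries that are themselves optional.

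The understated interim spread is conditional on an SD being shown. Its direction holds unless prediction is perfect. Its size depends on between-visit correlations and a dropout pattern that the documents do not give. The primary test, its interval and p-value, the final alpha and the tested secondary analyses do not change.

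**What to change.** 1. In 5.5.2.2 and 5.6.7, delete the median substitution. Select the IES children from the 100 imputed datasets, fit the model in each and combine by Rubin's rules, as 5.3 does for the Per-protocol Set. Keep the 5.6.7 non-responder override for treatment failure or death.
2. In 5.3, do not present the SD of per-child medians as the SD of the scores. Label it for what it is, and show the observed-data n, mean and SD beside it at each visit. Do not substitute the averaged within-dataset SD, which can be well too high in the small sham arm at the interim.
3. In the last paragraph of 5.6.7, state that in an early final analysis the tested HFMSE and upper limb analyses are the combined multiple-imputation analyses on the ITT Set, and that the IES versions are exploratory.

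The cost is minor programming and exploratory IES standard errors that rise by about 0.4% to 11% (1/0.996 to 1/0.902). The observed sham SD will be imprecise: with 17 of 42 children it varies by about √(1/32 − 1/82) = 14% around the full-data SD in a single trial, assuming normal data. Its n should therefore always be shown.
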